9.3 EXCLUSION CRITERIA

Any one (1) of the following criteria will disqualify a potential subject from participation in the study:

1. Subject is entered in another investigational drug, biologic, or device study or has been treated with an investigational product within 12 months post-operative.
2. Subjects who are < 3 months post-operative.

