7. OBJECTIVE(S)

7.1 PRIMARY OBJECTIVE

The primary objective of this study is to assess the safety and performance post-market of the PEEK Anchors (DYNOMITE[®], SPYROMITE[®], RAPTORMITE[®], FOOTPRINT[®] ULTRA PK SL) in extremities over a time period of 6 months after intervention.

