9.6 ENROLLMENT

For screening, only information available in the medical records will be reviewed. Once a potential subject has been identified, all inclusion criteria and none of the exclusion criteria have been met, and the informed consent process has been completed or a waiver of consent has been granted by IRB/EC, the subject will be considered enrolled and assigned a consecutive Subject

CONFIDENTIAL AND PROPRIETARY

This document contains information that is confidential and proprietary to Smith & Nephew PLC and Smith & Nephew, Inc. and is intended for use only by Smith & Nephew and its manufacturer. It shall not be reproduced or copied in whole or in part, nor shall the contents be disclosed by any means without prior written permission from Smith & Nephew, nor shall anyone make any use of it that is contrary to the expressed or implied wishes of Smith & Nephew.

Study Protocol—Device	
Safety and Performance of PEEK Anchors (DYNOMITE°, SPYROMITE°, RAPTORMITE°, FOOTPRINT° ULTRA PK SL) in Extremities	Number: 2018.15.SMD.PEEK.RET.EXT
	Version: 2.0 05Dec2018
	Page: Page 24 of 54

Identification (ID) number. Enrollment and assigned Subject ID will be documented on the Screening and Enrollment Log. For bilateral subjects, only one Subject ID will be assigned.

Any subject who signs an informed consent or has a waiver of informed consent and is subsequently identified as not meeting the required entry criteria is considered to be a screen failure. Demographic information must be captured in the appropriate Case Report Form (CRF) and the reason for screen failure will be documented on the Screening and Enrollment Log.

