10.2 STUDY ENDPOINTS

10.2.1 Primary Endpoint

Clinical success rate (%) of the study devices in extremities at 6 months post-operative with clinical success defined as extremity repairs without signs of device failure and/or re-intervention as assessed by the surgeon.

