12.2 ANALYSIS POPULATIONS

The following analysis populations will be used for this study:

- **Safety Population (SAF):** This includes all subjects who enroll in the study who had previously undergone repair in the extremities using any of the PEEK anchors: RAPTORMITE[°], DYNOMITE[°], SPYROMITE and FOOTPRINT[°] ULTRA PK SL.
- **Per-Protocol Population (PP):** This includes all subjects in the Safety Population, who have no significant protocol deviations and who meet all the inclusion/exclusion criteria. Deviations considered as significant will be defined and finalized prior to database lock.

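### Exclusion 1 depends on events after the index surgery, so a repair that has already failed can be dropped from every success rate and safety summary

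*Combined protocol and SAP*

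**What the plan says.** Section 9.3 (repeated in the synopsis) opens with "Any one (1) of the following criteria will disqualify a potential subject from participation in the study". The first criterion has two limbs, entry in another investigational study and treatment with an investigational product; its text ends "device study or has been treated with an investigational product within 12 months post-operative". Nothing confines it to the subject's status at or before the index operation.

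Eligibility is judged retrospectively. Section 9.6 states: "For screening, only information available in the medical records will be reviewed". The chart that shows the exposure can therefore also show how the repair fared.

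The primary endpoint (section 10.2.1) is the 6-month rate, with "clinical success defined as extremity repairs without signs of device failure and/or re-intervention as assessed by the surgeon". Section 10.2.2 uses the same definition at 12 months.

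Section 12.2 describes the safety population thus: "This includes all subjects who enroll in the study who had previously undergone repair in the extremities". The per-protocol population is a subset of it. Section 12.3 bases the 6-month rate on the per-protocol set, with the safety set as sensitivity analysis. Section 12.3.2 uses the safety set at 12 months, and section 12.4 uses it for the safety summaries. For an excluded subject, section 9.4 asks only that the reason be recorded in the source documents and on the log.

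**The concern.** An entry criterion should be settled by the time the outcome starts to accrue. This one is read over the whole 12 months in which the outcome occurs, and it may be a consequence of the outcome: a failed repair is a plausible reason to be offered an investigational product or to enter a revision study.

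Take a subject whose anchor fails at month 4 and who receives an investigational product at month 8. The 6-month outcome was fixed before the exposure, yet the subject is disqualified. The primary objective concerns performance "in extremities over a time period of 6 months after intervention", so an event in months 7 to 12 should not decide who counts towards it.

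At stake are the pooled and per-anchor success rates and the safety summaries. Section 9.1 prescribes enrolment in order of surgery date to limit selection bias; exclusion 1 opens another route for it. The documents give no reason for the post-operative window.

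**Working it through.** **The plan's own figure.** Section 13 assumes 91% success and states a probability of 15.2% (20 per anchor) to above 95% (120 per anchor) for the target precision of 80% to 100%. With the exact interval and a full width of at most 22 points (twice the 11 points from 80% to 91%), the probability is 0.91^20 = 15.16% at n = 20 and about 100% at n = 120, so the stated range reproduces on that criterion. It does not depend on exclusion 1. It is used here only for the 91% and the group sizes.

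**Can an excluded failure re-enter?**
1. A chart shows a failure, then an investigational exposure, both within 12 months of surgery.
2. Section 9.3 disqualifies the subject, who is not enrolled under section 9.6.
3. The safety set contains enrolled subjects only, and the per-protocol set is part of it, so the subject is in neither.
4. All rates in sections 12.3 and 12.3.2 and all summaries in section 12.4 use one of these sets. No planned analysis adds excluded subjects back.

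**Effect on the rate.** Let p be the true success rate, f the share of failures removed and g the share of successes removed. Then

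observed rate = p(1 − g) / [p(1 − g) + (1 − p)(1 − f)].

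The documents give neither f nor g; the values below are assumptions. With p = 0.91:

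| f | g | Calculation | Observed rate |
|---|---|---|---|
| 5% | 0 | 0.91 / (0.91 + 0.0855) | 91.4% |
| 10% | 0 | 0.91 / (0.91 + 0.081) | 91.8% |
| 20% | 0 | 0.91 / (0.91 + 0.072) | 92.7% |
| 5% | 5% | 0.8645 / (0.8645 + 0.0855) | 91.0% |
| 5% | 10% | 0.819 / (0.819 + 0.0855) | 90.5% |

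The sign of the bias is the sign of f − g.

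**In subjects.** At the minimum of 80 the expected number of failures is 0.09 × 80 = 7.2, so 5% to 20% of them is 0.4 to 1.4 subjects.

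**One removed failure, exact 95% intervals.**
- n = 20: 18/20 = 90.0% (68.3% to 98.8%) becomes 18/19 = 94.7% (74.0% to 99.9%).
- n = 120: 109/120 = 90.8% (84.2% to 95.3%) becomes 109/119 = 91.6% (85.1% to 95.9%).

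**The case against.** The strongest reply concerns direction and size. Exclusion 1 covers any investigational drug, biologic or device study, with no link to the operated joint. Subjects in unrelated studies leave whatever their repair did, and a failure revised with a marketed product stays in as a failure. A reader might infer that the bias is always favourable. The documents do not support that: equal removal gives none, and the last row of the table goes the other way. The n = 20 example removes half of the failures; it shows what one subject is worth, not what to expect. All this stands.

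A reader might also infer that section 9.6 turns someone enrolled at 3 months and exposed later into a screen failure. That section says a subject who "is subsequently identified as not meeting the required entry criteria is considered to be a screen failure". This reads most naturally as ineligibility at entry that is discovered afterwards; it does not clearly reach a new exposure.

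Nor is it certain that every affected subject is lost. The per-protocol definition adds compliance with the entry criteria to the safety set. That suggests the safety set might hold an enrolled subject who breaches one, whereas section 9.6 points to screen failure. The route is unsettled and covers only subjects already enrolled. The log would also give the number removed, so a worst-case bound could be calculated, although none is planned.

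The wording is ambiguous too: the 12-month phrase may limit only the treatment limb and not the study-entry limb. On neither reading is the criterion confined to events before surgery.

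Finally, excluding other investigational exposure helps to attribute outcomes to the anchor. That is a fair aim, but it does not justify discarding a failure that came before the exposure.

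**Conclusion.** The defect holds: eligibility is conditioned on events inside the outcome window, and a failure that precedes the exposure can drop out of the 6- and 12-month rates and the safety summaries with no planned analysis that reliably restores it.

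The documents establish neither direction nor size. The bias is upward only if failures meet the criterion more often than successes. Assuming that 5% to 20% of failures and no successes are removed, 91% would read 91.4% to 92.7%, a shift of 0.4 to 1.7 points and small against the planned 80% to 100% interval. The per-anchor rates at the minimum of 20 are more exposed, since one lost failure there can move the estimate by 4.7 points (94.7 − 90.0). The change is worth making because it is cheap and because the planned analyses would not show whether the bias had occurred.

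**What to change.** 1. Limit exclusion 1 to subjects who, at the index surgery, were in another investigational study or under treatment with an investigational product other than the study anchors. The carve-out is needed because section 9.1 calls the anchor the investigational device and sections 14.1.1 to 14.1.4 use the investigational-product term in defining anchor-related events; read literally, the sentence would otherwise exclude everyone.
2. Retain subjects first exposed after surgery, record the exposure date on the CRF, and classify them by the endpoint definition in the main analysis. Any failure or re-intervention dated before the exposure then counts as a failure.
3. Add a sensitivity analysis that omits from the rate at a given time point only those subjects who were exposed before that time point without a prior failure.
4. Report the number of subjects excluded under criterion 1.

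The cost is one eligibility sentence (in section 9.3 and the synopsis), one CRF date, one table and one reported count. It is lowest before enrolment starts; section 23.1.3 says version 2.0 itself was to take effect before then. The downside is that a few retained subjects may have later outcomes influenced by the other product, which the sensitivity analysis would show.

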9.4 SCREENING

Participating study sites are required to document all screened subjects considered for inclusion in this study. If a subject is excluded from the study, the reasons for exclusion will be documented in the subject's source documents and noted on the Screening and Enrollment Log.

9.5 INFORMED CONSENT

Study sites will obtain Institutional Review Board (IRB/Ethics Committee (EC)) approval for this study before any study specific activities are performed.

Due to the retrospective nature of the study, a waiver of informed consent for study participation will be requested from the IRB/EC for those subjects who meet eligibility criteria as only retrospective data set will be collected for these subjects. No prospective visits will be performed.

A waiver or alteration of the requirements for obtaining informed consent can occur under any of the following three provisions set forth by the Department of Health and Human Health Services:

Research in general: an IRB may waive or alter the requirement of informed consent under 45 CFR 46.116(d), provided that the IRB finds and documents that all of the following four conditions are met:

CONFIDENTIAL AND PROPRIETARY

This document contains information that is confidential and proprietary to Smith & Nephew PLC and Smith & Nephew, Inc. and is intended for use only by Smith & Nephew and its manufacturer. It shall not be reproduced or copied in whole or in part, nor shall the contents be disclosed by any means without prior written permission from Smith & Nephew, nor shall anyone make any use of it that is contrary to the expressed or implied wishes of Smith & Nephew.

Study Protocol—Device	
Safety and Performance of PEEK Anchors (DYNOMITE [®] , SPYROMITE [®] , RAPTORMITE [®] , FOOTPRINT [®] ULTRA PK SL) in Extremities	Number: 2018.15.SMD.PEEK.RET.EXT
	Version: 2.0 05Dec2018
	Page: Page 23 of 54

1. the research involves no more than minimal risk to the participants;
2. the waiver or alteration will not adversely affect the rights and welfare of the participants;
3. the research could not practicably be carried out without the waiver or alteration; and
4. Whenever appropriate, the participants will be provided with additional pertinent information after participation.

If an IRB/EC waiver is not granted, then informed consent shall be obtained from all study subjects according to ISO 14155 guidelines and all applicable national regulations. If waiver of consent is not approved, potential subjects must be informed as to the purpose of the study and the potential risks and benefits known or that can be reasonably predicted or expected as described in the written consent form. The subject, or their legally authorized representative, will then **read, sign, and personally date** the IRB/EC approved informed consent document(s) (see below for difficulties with reading and writing). Additionally, the individual who obtains consent from the subject will sign and date the informed consent document. A copy of the signed informed consent documentation will be provided to the subject, a copy will be placed in the subject’s medical record, and the original filed in the Investigator Site File (ISF).

If a subject refuses participation, no further information will be collected. Reason for exclusion should be noted on the Screening and Enrollment Log.

9.6 ENROLLMENT

For screening, only information available in the medical records will be reviewed. Once a potential subject has been identified, all inclusion criteria and none of the exclusion criteria have been met, and the informed consent process has been completed or a waiver of consent has been granted by IRB/EC, the subject will be considered enrolled and assigned a consecutive Subject

CONFIDENTIAL AND PROPRIETARY

This document contains information that is confidential and proprietary to Smith & Nephew PLC and Smith & Nephew, Inc. and is intended for use only by Smith & Nephew and its manufacturer. It shall not be reproduced or copied in whole or in part, nor shall the contents be disclosed by any means without prior written permission from Smith & Nephew, nor shall anyone make any use of it that is contrary to the expressed or implied wishes of Smith & Nephew.

Study Protocol—Device	
Safety and Performance of PEEK Anchors (DYNOMITE°, SPYROMITE°, RAPTORMITE°, FOOTPRINT° ULTRA PK SL) in Extremities	Number: 2018.15.SMD.PEEK.RET.EXT
	Version: 2.0 05Dec2018
	Page: Page 24 of 54

Identification (ID) number. Enrollment and assigned Subject ID will be documented on the Screening and Enrollment Log. For bilateral subjects, only one Subject ID will be assigned.

Any subject who signs an informed consent or has a waiver of informed consent and is subsequently identified as not meeting the required entry criteria is considered to be a screen failure. Demographic information must be captured in the appropriate Case Report Form (CRF) and the reason for screen failure will be documented on the Screening and Enrollment Log.

9.7 LOST TO FOLLOW-UP

A subject will be considered lost to follow-up if he/she did not return for follow-up per the study Investigator’s standard of care follow-up schedule. Information will be documented on the Case Report Form (CRF).

9.8 WITHDRAWAL

9.8.1 Withdrawal from the Study

The Investigator may withdraw subjects from the study for many reasons, including but not limited to the following:

- At the discretion of the Investigator.
- If the Investigator or the Sponsor stops the study for any reason and decides to withdraw subject(s) from the study.

For each case, information will be documented in the source document and the Case Report Form (CRF), detailing circumstances leading to the withdrawal. Subjects who are withdrawn will not be re-entered into the study at a later date. Data collected up to the point of withdrawal may be used but no additional data for that subject may be collected.

CONFIDENTIAL AND PROPRIETARY

This document contains information that is confidential and proprietary to Smith & Nephew PLC and Smith & Nephew, Inc. and is intended for use only by Smith & Nephew and its manufacturer. It shall not be reproduced or copied in whole or in part, nor shall the contents be disclosed by any means without prior written permission from Smith & Nephew, nor shall anyone make any use of it that is contrary to the expressed or implied wishes of Smith & Nephew.

Study Protocol—Device	
Safety and Performance of PEEK Anchors (DYNOMITE [®] , SPYROMITE [®] , RAPTORMITE [®] , FOOTPRINT [®] ULTRA PK SL) in Extremities	Number: 2018.15.SMD.PEEK.RET.EXT
	Version: 2.0 05Dec2018
	Page: Page 25 of 54

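### Section 9.8.1 lets the investigator withdraw an enrolled subject without any criterion and then stops data collection, so a chart outcome can influence who stays in the success rate

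*Combined protocol and SAP*

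**What the plan says.** Section 9.8.1 opens with "The Investigator may withdraw subjects from the study for many reasons, including but not limited to the following". The first listed reason is "At the discretion of the Investigator"; the second is a decision to stop the study. Revoked consent is not listed. On data, the section says: "Data collected up to the point of withdrawal may be used but no additional data for that subject may be collected". Each withdrawal is to be written up in the source document and CRF, "detailing circumstances leading to the withdrawal".

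The surrounding design matters:

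- Section 9.5: "No prospective visits will be performed". A consent waiver will be requested, and a consent route is set out in case it is refused.
- Section 9.1: enrolment runs consecutively by date of surgery, oldest first, as a guard against selection bias.
- Section 9.3 excludes "Subjects who are < 3 months post-operative", so entry is possible from 3 months onward.
- Section 10.2.1: the primary endpoint is the 6-month success rate, with "clinical success defined as extremity repairs without signs of device failure and/or re-intervention as assessed by the surgeon".
- Sections 12.2 and 12.3: the 6-month rate is analysed in the per-protocol population, with the safety population (everyone enrolled with a study anchor) as sensitivity analysis. The 12-month rate uses the safety population. Neither section says how a withdrawn subject, or one without a recorded status, enters the numerator or denominator.

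**The concern.** The withdrawal rule suits a prospective trial, where leaving spares a subject further visits. Here there are no study visits to be spared. The people who may remove a subject work from the record that holds the result, and the result is itself the surgeon's judgement.

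Sequential enrolment prevents choosing subjects by outcome at entry. A criterion-free exit after entry reopens that choice. If withdrawal comes before implant status is abstracted, the status is then barred from collection. The safety population still contains the subject but has no outcome to count. With as few as 20 subjects per anchor, one or two such withdrawals visibly change the reported rate.

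**Working it through.** **1. Inputs.** Assumed success 91% with a CI of 80% to 100%, 20 to 120 subjects per anchor, 80 to 480 in total (section 13). Two-sided 95% Clopper-Pearson interval (section 12.3). The documents give no withdrawal rate, so the withdrawal fractions below are assumptions. It is also an assumption that withdrawn subjects leave the denominator.

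**2. The plan's own figure.** Section 13 gives a probability of 15.2% at n=20 and above 95% at n=120 of reaching the planned precision. Take the rule that the half-width is at most 91 − 80 = 11 points. At n=20, 20/20 gives 83.2% to 100% (half-width 8.4) and qualifies; 19/20 gives 75.1% to 99.9% (half-width 12.4) and does not. The probability is 0.91^20 = 15.16%. At n=120 it is about 100%. Both agree with the plan. If the rule is instead that the lower limit is at least 80%, the values are 15.2% and 92.7%. This step only confirms the interval method; the plan's figure does not depend on the withdrawal rule.

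**3. Effect of withdrawing failures.** With x recorded successes among m remaining subjects, the rate is x/m. The limits are the 2.5% quantile of Beta(x, m−x+1) and the 97.5% quantile of Beta(x+1, m−x).

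| Enrolled / failures | Failures withdrawn | Recorded | Rate | 95% CI |
|---|---|---|---|---|
| 20 / 2 | 0 | 18/20 | 90.0% | 68.3–98.8 |
| 20 / 2 | 1 | 18/19 | 94.7% | 74.0–99.9 |
| 20 / 2 | 2 | 18/18 | 100% | 81.5–100 |
| 80 / 7 | 0 | 73/80 | 91.3% | 82.8–96.4 |
| 80 / 7 | 3 | 73/77 | 94.8% | 87.2–98.6 |
| 80 / 7 | 7 | 73/73 | 100% | 95.1–100 |
| 120 / 11 | 0 | 109/120 | 90.8% | 84.2–95.3 |
| 120 / 11 | 5 | 109/115 | 94.8% | 89.0–98.1 |

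**4. Expected size over a range.** Suppose each failure is withdrawn unrecorded with probability w. The expected rate at a true 91% is about 0.91/(1 − 0.09w):

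| w | Expected rate | P(lower limit ≥ 80%), n=20 |
|---|---|---|
| 0 | 91.0% | 15.2% |
| 25% | 93.1% | 24.7% |
| 50% | 95.3% | 39.3% |
| 100% | 100% | 90.1% |

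With a true rate of 80% and w=50%, the expected rate is 0.80/(1 − 0.20 × 0.5) = 88.9%. At n=80 the chance of a lower limit of at least 80% rises from 1.3% to 45.6%.

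**5. The other direction.** Starting from 18/20, withdrawing two successes gives 16/18 = 88.9% (65.3–98.6). The rule has no direction of its own.

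**6. The proposed count.** If withdrawn subjects without a status count as non-successes, withdrawing either or both failures leaves 18/20 = 90.0% (68.3–98.8). If instead two successes are withdrawn, the count is 16/20 = 80.0% (56.3–94.3), which is conservative.

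**The case against.** The plan has real safeguards.

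- Each withdrawal is documented, screened charts are logged, and section 16 requires monitoring of data completeness.
- Table 1 puts eligibility, operative data and implant status in the same 6-month chart review, so the gap between enrolment and abstraction may be short.
- Section 14 requires device- and procedure-related events and device deficiencies to be recorded from surgery onward, and events leading to revision to be reported whatever their cause.
- The safety population keeps everyone enrolled.
- Section 12 promises a SAP before database lock that could set a counting rule.

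These reduce the risk, and many failures would surface as safety events. None of them limits the reason for withdrawal, requires a withdrawn subject's implant status to be abstracted, or places that subject in the success rate. A later SAP can define the denominator but cannot recover data that were barred from collection.

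A reader might infer more than the text supports:

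- *That every outcome is already known.* Entry is allowed from 3 months, and the 6-month window opens at day 182 − 90 = 92 and the 12-month window at day 365 − 90 = 275. Some outcomes may not exist at enrolment.
- *That the bias can only be upward.* Step 5 shows otherwise; it is upward only if failures are the ones withdrawn.
- *That withdrawal never protects anyone because consent is waived.* The waiver is only requested, and where consent is required a subject may revoke it.
- *That 100% (81.5–100) passes a test the true data would fail.* The 80% to 100% range is a precision expectation in a study without hypothesis tests, not a pass mark.

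**Conclusion.** The point stands as a gap in the rule. Section 9.8.1 permits outcome-dependent exclusion after enrolment, and the analysis sections do not repair it. Nothing in the documents shows that investigators would use it in that way.

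The size depends on how many failures leave unrecorded. One withdrawn failure moves an anchor with 18/20 by 4.7 points. Three withdrawn failures move a pooled 73/80 by about 3.5 points (94.8% − 91.3%). Both figures assume that only failures are withdrawn, that this happens before their status is abstracted, and that they then leave the denominator, which the plan neither states nor rules out. It should be corrected, because the change is small and removes an avoidable source of bias.

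**What to change.** **In section 9.8.1:**

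- Delete "At the discretion of the Investigator" and the wording that makes the list of reasons open-ended.
- Limit withdrawal to revoked consent, at sites where consent was required, or closure of the study or site.
- Replace the bar on further collection with a requirement to abstract 6- and 12-month implant status from the existing chart for every enrolled subject, as far as consent allows.

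**In section 12.3 and the SAP:**

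- In the safety-population sensitivity analysis, keep withdrawn subjects without a recorded status in the denominator as non-successes.
- List each withdrawal by site, date and reason.

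**Cost.** The section 9.8.1 change is a protocol amendment. Under section 17 it needs approval by the signatories and the IRB, at up to 15 sites, and amendments after study start are meant to be exceptional. No additional subjects or visits are needed. The sensitivity estimate becomes less favourable for any withdrawn subject who was in fact a success. At n=20 that is 5 points per subject (1/20), so the result should be read as a conservative bound. Abstracting status for everyone should keep such subjects few.
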